7.3.2 BMS-986226 Dose-limiting Toxicities

For the purpose of guiding dose escalation, DLTs will be defined based on the incidence, intensity, and duration of AEs for which no clear alternative cause is identified. The DLT period will be 35 days (5 weeks).

In the Preliminary Safety Cohorts, participants who have received 1 dose of BMS-986226 and have completed, or who discontinued due to a DLT in the 4-week DLT period, will be considered as DLT-evaluable participants for BMS-986226 monotherapy.

In Part A, participants who have received 2 doses of BMS-986226 and have completed, or who discontinued due to a DLT in the 5-week DLT period, will be considered as DLT-evaluable participants for BMS-986226 monotherapy.

In Parts B, C, D and E, participants receiving either 1 dose of BMS-986226 or 2 doses of either nivolumab or ipilimumab, or participants who discontinued due to a DLT in the 5-week combination treatment DLT period, will be considered as DLT-evaluable participants for combination treatment. Participants who withdraw from the study during the DLT evaluation period or have received less than 2 doses for reasons other than a DLT in the monotherapy (Part A) or 1 dose in combination therapy (Parts B, C, D, E), will not be considered as DLT-evaluable participants in Part A, who are dose delayed during the DLT evaluation period for reasons other than a DLT could be considered as DLT-evaluable participants if they receive at least 2 doses of therapy.

For the purpose of participant management, any AE that meets DLT criteria, regardless of the cycle in which it occurs, will lead to discontinuation of study treatment (except as defined in Section 7.3.5). Participants who withdraw from the study during the 5-week DLT evaluation period for reasons other than a DLT may be replaced with a new participant at the same dose

level. The incidence of DLT(s) during the 5-week DLT evaluation period will be used in dose escalation decisions through application of the BLRM/BLRM-Copula model. AEs occurring after the DLT period will be considered to enhance the robustness of BLRM/BLRM-Copula prediction, upon agreement between the Sponsor, Medical Monitor/Study Director (or designee), and investigators.

Participants experiencing a DLT will enter the safety follow-up period of the study. DLTs occurring after the 4-week DLT observation period for the Preliminary Safety Cohorts or 5-week DLT observation period for Parts A, B and C will be accounted for in determining the MAD for the combination part.

AEs will be graded according to the NCI CTCAE v4.03²⁷, as listed below:

A. Hepatic Non-hematological DLT

Any one of the following study treatment-related events will be considered a hepatic DLT:

- Any Grade \geq 3 elevation of AST, ALT, or total bilirubin.
- Grade 2 AST or ALT with symptomatic liver inflammation (eg, right upper quadrant tenderness, jaundice, pruritus).
- AST or ALT > 3× ULN and concurrent total bilirubin > 2× ULN without initial findings of cholestasis (elevated serum alkaline phosphatase [ALP] [eg, findings consistent with Hy's law or FDA definition of potential drug-induced liver injury or potential drug-induced liver injury [p-DILI]). Note that this special category of DLT uses ULN rather than Common Toxicity Criteria (CTC) grade for definition.

B. Non-hepatic Non-hematological DLT

Any of the following events will be considered a non-hepatic non-hematological DLT:

- Any Grade 2 drug-related uveitis or eye pain or blurred vision that does not respond to topical therapy and does not improve to Grade 1 severity ≤ 2 weeks *or* requires systemic treatment.
- Grade 3 drug-related uveitis, pneumonitis, bronchospasm, myocarditis, neurologic toxicity, hypersensitivity reaction, or infusion reaction of any duration will require discontinuation.
- Any Grade 3 or greater nondermatologic, nonhepatic nonhematological study treatment-related toxicity will be considered a DLT, with the following specific exceptions:
 - Grade 3 or Grade 4 electrolyte abnormalities that are not complicated by associated clinical adverse experiences, last \leq 72 hours, and either resolve spontaneously or respond to conventional medical intervention
 - Grade 3 nausea, vomiting, or diarrhea that lasts less than 72 hours (without steroid therapy) and either resolves spontaneously or responds to conventional medical intervention
 - Isolated Grade 3 elevation of amylase or lipase not associated with clinical or radiographic evidence of pancreatitis
 - Isolated Grade 3 fever not associated with hemodynamic compromise (eg, hypotension, clinical or laboratory evidence of impaired end-organ perfusion or with other symptoms of infusion-related reactions that returns to ≤ Grade 1 with standard treatment in ≤ 1 hour

Revised Protocol No.: 04 Date: 31-May-2019

- Grade 3 endocrinopathy that is well controlled by hormone replacement
- Grade 3 tumor flare (defined as pain, irritation, or rash that localizes to sites of known or suspected tumor)
- Grade 3 fatigue for \leq 7 days
- Grade 3 infusion reaction that returns to Grade 1 in \leq 1 hour

C. Dermatologic DLT

- Grade 3/4 rash if no improvement (ie, resolution to Grade ≤ 1) after a 1-week to 2-week infusion delay. Participants who have not experienced a Grade 3 drug-related skin AE may resume treatment in the presence of Grade 2 skin toxicity.
- Grade 4 rash of any duration

D. Hematologic DLT

- Grade 4 neutropenia \geq 5 days in duration
- Grade 4 thrombocytopenia or Grade 3 thrombocytopenia with clinically significant bleeding or any requirement for platelet transfusion
- Grade 4 anemia not explained by underlying disease
- Grade 4 febrile neutropenia
- Grade 3 febrile neutropenia that lasts > 48 hours
- Grade \geq 3 hemolysis (i.e., requiring transfusion or medical intervention such as steroids)

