5.1.2 Treatment Phase

The treatment phase in the Preliminary Safety Cohort and Part A consists of up to six 4-week treatment cycles (1 cycle = 28 days). In the Preliminary Safety Cohort and Part A, each treatment cycle will consist of BMS-986226 monotherapy for a total of 24 weeks.

Dose levels for Parts B and C will be determined based on all available safety (clinical and laboratory) and PK data, as well as changes in peripheral target engagement markers (eg, ICOS

downregulation on T cells and ICOS + B cells) from previous and completed portion of current cohorts, and will be guided by the BLRM/BLRM-Copula model whenever applicable.

In Parts B1 and C1, 4 week cycles will be used, such that BMS986226 + nivolumab or ipilimumab will be administered starting on Cycle 1 Day 1. Nivolumab and ipilimumab will be administered on Day 1 of each cycle. BMS-986226 will be administered Q12W, or on Day 1 of every third cycle (Cycle 1 Day1, Cycle 4, Day1, Cycle 7 Day1, etc.). Participants on Parts B1 and C1 may continue treatment for up to a total of 2 years.

The treatment phase in Parts B2 and C2 will consist of BMS-986226 + nivolumab or ipilimumab administered on Day 1 of each cycle and will be enrolled if additional safety, PK, or PD data is required to optimize dose and/or schedule selection. In parts B2 and C2 BMS-986226 will be administered Q4W and participants may continue treatment for a total of 2 years.

Following each treatment cycle, the decision to treat a participant with additional cycles of study treatment will be based on tumor assessment evaluations performed every 8 weeks $(Q8W \pm 1 \text{ week})$ and completed before the first dose in the next cycle. Tumor progression or response endpoints will be assessed using Response Evaluation Criteria In Solid Tumors (RECIST) v1.1 (Appendix 5) or PCWG3, for prostate only (Appendix 11).

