7.1 Treatments Administered

The selection and timing of dose for each participant are presented in Table 7.1-1.

Table 7.1-1:Selection and Timing of Dose per Part

Study Treatment	Dose Level	Frequency of Administration	Route of Administration	Infusion time (Minute)
Preliminary Safety (Cohorts and Part A			
BMS-986226	2, 8, 25, 80, 200, 400, 800 mg	Q4W	IV	30
Part B1				
Nivolumab	480 mg	Q4W		30
BMS-986226	3 Doses evaluated by BLRM-copula, PK/PD	Q12W	IV	30
Part B2				
Nivolumab	480 mg	Q4W	IV	30
BMS-986226	3 Doses evaluated by BLRM-copula, PK/PD	Q4W	IV	30
Part C1				
Ipilimumab	3 mg/kg ^a	Q4W		30
BMS-986226	3 Doses evaluated by BLRM-copula, PK/PD	Q12W	IV	30

Revised Protocol No.: 04 Date: 31-May-2019

Study Treatment	Dose Level	Frequency of Administration	Route of Administration	Infusion time (Minute)
Part C2				
Ipilimumab	3 mg/kg ^a	Q4W		30
BMS-986226	3 Doses evaluated by BLRM-copula, PK/PD	Q4W	IV	30
Part D				
Nivolumab	480 mg	Q4W	IV	30
BMS-986226	PK/PD from Part B	TBD	1 V	30
Part E				
Ipilimumab	3 mg/kg ^a	Q4W	IV	30
BMS-986226	PK/PD from Part C	TBD	IV	30

Table 7.1-1:Selection and Timing of Dose per Part

^a Weight collected at baseline/screening should be used to calculate ipilimumab dose unless weight has changes more than +/- 10% from baseline on C1D1

Note: In Parts B, C, D, and E a 30-minute infusion of either nivolumab or ipilimumab will be followed by a 30-minute observation period, followed by a 30-minute infusion of BMS-986226. In all parts, participants will be observed for at least 60 minutes following the completion of BMS-986226 infusion due to the potential risk of, and to monitor for, infusion reactions.

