7.3.1 Treatment Delay

Participants who experience a DLT must have the study treatment held. Participants who are required to permanently discontinue both study treatments are listed in Section 8.1. In addition, all Grade 2 hepatic, pulmonary, renal, GI, and neurological AEs should be evaluated and managed per the toxicity management algorithms (Appendix 6). Participants not meeting guidelines for

permanent discontinuation will be permitted to resume study treatment based on the criteria specified below in Section 8.1.1. Participants eligible to resume study treatment will resume study treatment at the visit following their last received dose.

In all cohorts, if there is a delay in dosing of BMS-986226 alone or in combination with nivolumab or ipilimumab, between 1 and 12 days, the procedures at the original scheduled visit should be performed as soon as possible. If the delay is more than 12 days, the visit and dose will be considered missed; the procedures at the next scheduled visit should be performed, and subsequent BMS-986226 doses will follow every 4 weeks.

Extensions to the period of dose delays may be granted for individual participants on a case-by-case basis after specific consultation and agreement between the investigator and BMS Medical Monitor/Study Director (or designee) in settings where benefit/risk may justify continued study treatment (eg, participant deriving clinical benefit who requires prolonged steroid taper for the management of non-DLT -drug-related- AEs or experiences delays for the management of a nondrug-related AE).

The end of cycle tumor assessments (ie, CT/MRI, PET, etc) will continue on a Q8W schedule relative to the participant's first dose regardless of any study treatment delay incurred.

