4 BLRM-COPULA MODEL SETUP FOR BMS-986226 AND NIVOLUMAB OR IPILIMUMAB COMBINATION

For Parts B and C of this study, the BLRM-Copula model will be used to evaluate the starting dose and to guide the subsequent doses of BMS-986226 in combination with nivolumab or ipilimumab.

The BLRM-Copula model incorporates the latest information, including monotherapy information from Part A and any available toxicity information in completed portion of Parts B and C, available at the time of dose recommendation. In other words, the model concept covers both the starting doses and any subsequent doses of BMS-986226 in combination with nivolumab or ipilimumab in Parts B and C. Specifically, the starting dose of BMS-986226 in Parts B and C will be guided using the BLRM-Copula model, incorporating available single-agent toxicity profiles of BMS-986226 from the preliminary safety cohorts and Part A and nivolumab or ipilimumab. Any subsequent dose of BMS-986226 in Parts B and C will be evaluated using the BLRM-Copula model, incorporating of BMS-986226, nivolumab or ipilimumab and any available combination toxicity profiles from on-going Parts B and C.

In any case, the dose of BMS-986226 in combination with nivolumab or ipilimumab in Parts B and C will not exceed the maximum administered dose for BMS-986226 monotherapy in Part A. In summary, the doses of BMS-986226 in Parts B and C (combination with nivolumab or ipilimumab) will be determined using all available safety (clinical and laboratory), PK, and target engagement data, and the modelling recommendation using the BLRM-Copula model. The toxicity profiles of both BMS-986226 monotherapy and nivolumab or ipilimumab monotherapy, to be incorporated in the BLRM-Copula model, will be discussed in upcoming subsections. We introduce briefly the technical background of the BLRM-Copula model in the following paragraph.

A copula-type model can be used to cover all general combination cases, including additive and synergistic effects. The combination of the 2 treatments will be explored using a Bayesian hierarchical model by utilizing the toxicity profiles of the single agents as prior marginal profiles for the combination. The following copula-type model⁴ will be used to describe the probability p_{ij} of toxicity when dose level *i* of agent A and dose level *j* of agent B are administered in combination:

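### Section 7.3.2 counts Parts B to E participants as DLT-evaluable on either drug alone and without a completed window, so the modelled combination DLT rate can lean slightly low

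*Combined protocol and SAP*

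**What the plan says.** Section 7.3.2 sets three evaluability rules in turn.

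- Preliminary Safety Cohorts: "In the Preliminary Safety Cohorts, participants who have received 1 dose of BMS-986226 and have completed" the 4-week window, or discontinued for a DLT.
- Part A: "In Part A, participants who have received 2 doses of BMS-986226 and have completed" the 5-week window, or discontinued for a DLT.
- Combination parts: "In Parts B, C, D and E, participants receiving either 1 dose of BMS-986226 or 2 doses of either nivolumab or ipilimumab", or discontinued for a DLT. No completion condition is stated.

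The next sentence excludes participants who withdraw from the study during the window. It also excludes those below a dose minimum, given for the combination as "or 1 dose in combination therapy (Parts B, C, D, E), will not be considered as DLT-evaluable participants". It names no drug for that minimum and runs straight into a clause about dose delays in Part A.

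Section 7.3.2 feeds DLT incidence over the 5-week window to the model. Appendix 10, Section 4, gives the model's role: "For Parts B and C of this study, the BLRM-Copula model will be used to evaluate the starting dose" and to guide later doses. On schedule, Section 5.1.2 says: "In parts B2 and C2 BMS-986226 will be administered Q4W". Two BMS-986226 doses therefore fall due within 35 days in those parts, against one in the Q12W parts B1 and C1.

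**The concern.** The wording lets three kinds of participant without a DLT count as full combination non-events.

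- (a) Two partner doses and no BMS-986226.
- (b) Both drugs at Cycle 1, then treatment stopped while remaining in the study. Section 8.2 keeps such participants in the study, so the withdrawal exclusion does not reach them.
- (c) In B2 or C2, one of the two BMS-986226 doses due in the window. Section 8.1 allows the partner to continue after BMS-986226 stops.

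The exclusion sentence does not resolve (a). If its one dose means BMS-986226, it contradicts the partner-only branch; if it means either drug, it leaves that branch open.

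Anyone who discontinues for a DLT in the window is evaluable anyway, so the loose rule can add only non-events. If the added participants carry less risk than those exposed as scheduled, the fitted DLT rate is too low. A dose can then pass the EWOC condition, a probability below 30% that the DLT rate is 33% or more, more easily than it should.

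**Working it through.** **The plan's own figures.** Section 10.1.2 gives detection probabilities for an AE with a 24% rate: 1 − 0.76^6 = 0.807 (stated about 80%) and 1 − 0.76^12 = 0.963 (stated 96%). For the interaction prior in Appendix 10, Section 4.1.4, a gamma with mean 1.2 and SD 0.5 has shape 5.76 and rate 4.8, so P(γ > 1) = 0.611 (stated 61%). All reproduce.

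**Expected rate in six participants, true rate 33%.** The partner-only risk is assumed equal to the Grade 3–4 rates used for the priors. For ipilimumab 3 mg/kg (Table 4.1.3-1) this is (27 + 16 + 66 + 10)/(131 + 111 + 362 + 71) = 119/675 = 17.6%. For nivolumab 3 mg/kg (Table 4.1.2-1) it is 150/1146 = 13.1%. Both-drug participants are credited to Day 28 of 35 under constant hazard: 1 − 0.67^0.8 = 27.4%.

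- Ipilimumab only: (5 × 0.33 + 0.176)/6 = 30.4% with one affected; (4 × 0.33 + 2 × 0.176)/6 = 27.9% with two.
- Nivolumab only: 29.7% and 26.4%.
- Both drugs: 32.1% and 31.1%.

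**Effect on the cap.** The five-parameter copula was fitted by likelihood-weighting 4 million prior draws. The inputs were:

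- BMS-986226 prior from Table 1.2-1, updated with assumed monotherapy data: 0/3 at 25 mg, 0/6 at 80 mg, and 0/6 or 1/6 at 200 mg.
- Ipilimumab 50:50 mixture from Table 4.1.3-2, at 3 mg/kg with reference dose 10 mg/kg.
- Nivolumab prior from Table 4.1.2-2, at its reference dose.
- The gamma interaction prior above.

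With p the combination risk and q the partner risk, an ordinary non-event contributes (1 − p). A partner-only non-event contributes (1 − q), and a both-drug incomplete one contributes (1 − p)^0.8. An excluded participant contributes nothing. The table gives P(DLT rate ≥ 33%) at 2 DLTs in 6; paired values are for one and two affected.

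| Partner, BMS-986226 dose, monotherapy at 200 mg | As counted | Partner-only | Both drugs | Excluded |
|---|---|---|---|---|
| Ipilimumab, 80 mg, 0/6 | 0.151 | 0.162, 0.176 | 0.161, 0.172 | 0.210, 0.299 |
| Ipilimumab, 200 mg, 0/6 | 0.196 | 0.218, 0.247 | 0.207, 0.219 | 0.260, 0.350 |
| Nivolumab, 80 mg, 0/6 | 0.041 | 0.052, 0.066 | 0.044, 0.046 | 0.055, 0.073 |
| Nivolumab, 200 mg, 0/6 | 0.092 | 0.116, 0.148 | 0.097, 0.102 | 0.120, 0.156 |
| Ipilimumab, 80 mg, 1/6 | 0.230 | 0.257, 0.292 | 0.241, 0.254 | 0.296, 0.386 |
| Ipilimumab, 200 mg, 1/6 | 0.340 | 0.383, 0.436 | 0.354, 0.369 | 0.416, 0.508 |
| Nivolumab, 80 mg, 1/6 | 0.127 | 0.157, 0.194 | 0.133, 0.140 | 0.161, 0.206 |
| Nivolumab, 200 mg, 1/6 | 0.263 | 0.314, 0.376 | 0.273, 0.285 | 0.320, 0.388 |

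- Partner-only reweighting crosses 0.30 in one scenario, the last row. Both-drug reweighting crosses in none.
- Exclusion crosses in one scenario with one excluded and in three with two. A fourth, at 0.299, sits on the line within simulation error of about 0.002.
- Ipilimumab with 200 mg at 1/6 is above the cap throughout.

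Over 0 to 3 DLTs in 6 (32 cases), partner-only reweighting changes two cases with one affected and three with two, all with nivolumab. Those beyond the last row are at 3 DLTs in 6: 80 mg with 1/6 (0.270 to 0.327 or 0.396) and 200 mg with 0/6 (0.217 to 0.269 or 0.336). Both-drug reweighting changes none of the 32.

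**The case against.** The strongest reply is that the one group able to move a decision under reweighting, group (a), will be nearly empty. Both drugs are given in one session: the partner infusion is "followed by a 30-minute observation period, followed by a 30-minute infusion of BMS-986226". Section 7.3.1 says that for delays "between 1 and 12 days, the procedures at the original scheduled visit should be performed as soon as possible". Section 7.3.4 withholds all study treatment for the listed toxicities, so those delays do not produce partner-only dosing. Someone never given BMS-986226 could hardly meet its drug-related discontinuation criteria. This stands: partner-only dosing should be rare.

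A second reply is that, in a section about BMS-986226 DLTs, the one-dose minimum most naturally means BMS-986226. That may well be the intent. The change record for Revised Protocol 02 in Appendix 12 also describes the window as covering two partner doses and one BMS-986226 dose together. But the operative sentence still says the opposite, and a user of the section has to choose between them.

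Third, participants who stop treatment are still observed: Section 9.2.1 collects AEs to 100 days after the last dose. In (b) the missing partner dose falls on Day 29 of 35. This too stands, and it is why the both-drug figures barely move.

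A reader might go further and compare 2 DLTs in 4 with 2 in 6, without monotherapy data. For nivolumab with 80 mg the overdose probability then falls from 0.41 to 0.23. The documents do not support that as the size of the effect. Appendix 10, Section 4.1.1, makes the monotherapy posterior the BMS-986226 prior, and continued AE collection means an incomplete participant is not uninformative.

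**Conclusion.** The point holds as a minor fault in a stated rule. As written, Section 7.3.2 gives conflicting answers on partner-only exposure, requires no completed window in the combination parts, and ignores the second BMS-986226 dose due in B2 and C2. The modelled DLT rate for Parts B and C can therefore lean low through its denominator.

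Three stronger inferences are not supported.

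- DLTs are not lost from the count, because a DLT that leads to discontinuation in the window always makes the participant evaluable.
- Not everyone with an incomplete window gets in, because study withdrawals are excluded.
- The model effect does not extend to Parts D and E. They share the wording, but Section 5.1.2.4 monitors an aggregate 33% rate across all treated participants.

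The size rests on assumptions. The documents do not say how many participants would be affected, and the monotherapy data, the one or two affected in six and the 2 DLTs in six are all assumed. On those terms reweighting changes at most 1 of 8 cap decisions, and outright exclusion 1 to 3 of 8 as an upper bound before replacement. The model also guides rather than decides: the final dose rests on overall clinical assessment, using data from all treated participants. Confidence in the size is medium.

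**What to change.** Reconcile the two sentences of Section 7.3.2. Evaluability for the combination should require exposure to both BMS-986226 and the partner plus completion of the 35-day window, or a DLT within it. State which drug the one-dose minimum refers to. The sponsor should also state how many BMS-986226 doses count as sufficient for evaluability in the Q4W parts.

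Then align the replacement text for Parts B and C. The combination DLT paragraphs at the end of Section 5.1.2.3 allow replacement only for study withdrawal. Section 7.1.1 covers replacement of DLT-non-evaluable participants only for the Preliminary Safety Cohorts and Part A.

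The cost is wording in three places. A few more participants may become non-evaluable and be replaced. The evaluable-only rate may lean slightly high, because participants with a DLT always count while some without one drop out.

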- Once the DLT period of 5 weeks for 25 mg is completed, participant(s) treated at 2 mg that escalated to 8 mg or participant(s) treated with 8 mg may be offered the possibility to dose escalate at 25 mg

The decision to dose escalate may be allowed in select participants after discussion and agreement with the BMS Medical Monitor/Study Director (or designee), as long as the participant is tolerating treatment.

The decision to treat a participant with additional cycles of study treatment (up to a maximum of 24 weeks), will be based on safety, tolerability, and tumor assessment Q8W (± 1 week) prior to dose administration in the next cycle.

Part A

Dose escalation decisions in Part A of the study will be guided by Bayesian Logistic Regression Model (BLRM). Each participant will be administered IV doses of BMS-986226 per the cohort assignment as follows:

- 25 mg flat dose Q4W in 4-week cycles for up to 24 weeks of study treatment
- 80 mg flat dose Q4W in 4-week cycles for up to 24 weeks of study treatment
- 200 mg flat dose Q4W in 4-week cycles for up to 24 weeks of study treatment
- 400 mg flat dose Q4W in 4-week cycles for up to 24 weeks of study treatment
- 800 mg flat dose Q4W in 4-week cycles for up to 24 weeks of study treatment

A sentinel participant will be used for all cohorts of monotherapy in Part A and combination therapy in Parts B and C. The first participant in each cohort will receive the Cycle 1 Day 1 dose of study treatment and be observed for 5 days before additional participants (ie, Participant 2 onward) in that cohort receive study treatment.

The decision to treat a participant with additional cycles of study treatment (up to a maximum of 24 weeks), will be based on safety, tolerability, and tumor assessment Q8W (± 1 week) prior to dose administration in the next cycle.

Planned dose levels may be modified or intermediate dose levels added guided by the BLRM analysis with consideration of all available safety, PK, and PD data.

Once the safety (during the DLT evaluation) of a dose level has been established, additional participants (up to a total of 12) may be added at that dose level to better characterize the safety, PK, and PD profile.

Dose Escalation Decisions for Part A

The dose-escalation phase of the study will evaluate the safety and tolerability of BMS-986226 monotherapy based on DLTs using a BLRM model.

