During the dose-escalation phase, a set of approximately 3 participants will be treated initially at each specified dose level. Cohort tolerability assessment and subsequent dose recommendation will occur when at least 2 evaluable participants within a cohort have completed a 5-week DLT period. Any toxicities that occur beyond the 5-week DLT period will be accounted for in making dose level decisions and/or dose level modifications.

If the potential DLT occurring in the third evaluable participant regarding the specific dose level does not influence the dose recommendation by BLRM, the next dose level may proceed without waiting for the third participant to complete the corresponding DLT observation period after discussion and agreement between the Sponsor and investigators. Continuous re-assessment of dose recommendation, by BLRM in the monotherapy escalation phase, will be carried out for each dose level. Planned dose levels for dose escalation are provided in Table 5.1.2.1-1. Planned dose levels may be modified, or additional intermediate dose levels added, based upon the BLRM

analysis. Once the safety (during the DLT evaluation) of a monotherapy dose level has been established (Preliminary Safety Cohorts and Part A), additional participants (up to 12 total) may be added at that dose level to better characterize the safety, PK, and PD profile.

Dose Level	BMS-986226		
1	2 mg (Preliminary Safety Cohorts)		
2	8 mg (Preliminary Safety Cohorts)		
3	25 mg (Part A)		
4	80 mg (Part A)		
5	200 mg (Part A)		
6	400 mg (Part A)		
7	800 mg (Part A)		

 Table 5.1.2.1-1:
 Dose Escalation (Preliminary Safety Cohorts and Part A)

Dose-limiting Toxicities in Part A

For the purpose of guiding dose escalation, DLTs will be defined based on the incidence, intensity, and duration of AEs for which no clear alternative cause is identified. The DLT period will be 35 days (5 weeks) in Part A. Any toxicities that occur beyond the 5-week DLT period will also be considered in dose-level decisions.

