- Grade 4 drug-related endocrinopathy AEs, such as hyperthyroidism or hypothyroidism, or glucose intolerance, which resolve or are adequately controlled with physiologic hormone replacement (corticosteroids, thyroid hormones) or glucose-controlling agents, respectively, may not require discontinuation after discussion with and approval from the BMS Medical Monitor/Study Director (or designee).
- Any event that leads to delay in dosing lasting > 6 weeks from the previous dose requires discontinuation, with the following exceptions:
 - Dosing delays to allow for prolonged steroid tapers to manage study treatment-related AEs are allowed
 - Dosing delays lasting > 6 weeks from the previous dose that occur for nondrug-related reasons may be allowed if approved by the BMS Medical Monitor/Study Director (or designee).
- The assessment for discontinuation of nivolumab or ipilimumab should be made separately from the assessment made for discontinuation of BMS-986226. Although there is overlap among the discontinuation criteria, if discontinuation criteria are met for BMS-986226 but not for nivolumab or ipilimumab, treatment with nivolumab or ipilimumab may continue even if BMS-986226 is discontinued.
- If a participant in any of the nivolumab or ipilimumab/BMS-986226 combination arms meets criteria for discontinuation and the investigator is unable to determine whether the event is related to both or 1 of the study treatments, the participant should discontinue both nivolumab or ipilimumab and BMS-986226 and should be taken off the treatment phase of the study.

Refer to the Schedule of Activities (Section 2) for the data to be collected at the time of treatment discontinuation and follow-up and for any further evaluations that can be completed.

All participants who discontinue study treatment should comply with protocol specified follow-up procedures as outlined in Section 5.1.3. The only exception to this requirement is when a participant withdraws consent for all study procedures, including posttreatment study follow-up, or loses the ability to consent freely (eg, imprisonment, involuntarily incarceration for the treatment of either a psychiatric or a physical illness).

If study treatment is discontinued prior to the participant's completion of the study, the reason for the discontinuation must be documented in the participant's medical records and entered on the appropriate CRF page.

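### Part A's delay exception lets a participant count as DLT-evaluable although the second dose fell after the 35-day DLT window

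*Combined protocol and SAP*

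**What the plan says.** Section 5.1.2.1 fixes the window: "The DLT period will be 35 days (5 weeks) in Part A". Dosing is four-weekly at every Part A level, for example "25 mg flat dose Q4W in 4-week cycles for up to 24 weeks of study treatment".

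Section 7.3.2 defines the evaluable Part A participants as "participants who have received 2 doses of BMS-986226 and have completed, or who discontinued due to a DLT in the 5-week DLT period". It then makes an exception for Part A participants "who are dose delayed during the DLT evaluation period for reasons other than a DLT could be considered as DLT-evaluable participants". The only condition attached is the number of doses: they "could be considered as DLT-evaluable participants if they receive at least 2 doses of therapy". Neither sentence says when the second dose must be given, and no text lengthens the window for someone who is late.

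On delays, Section 7.3.1 keeps a short one within the same visit: if it is "between 1 and 12 days, the procedures at the original scheduled visit should be performed as soon as possible". Beyond that, "If the delay is more than 12 days, the visit and dose will be considered missed". Section 8.1 adds: "Any event that leads to delay in dosing lasting > 6 weeks from the previous dose requires discontinuation". Its exceptions are prolonged steroid tapers and sponsor-approved delays unrelated to drug.

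Section 10.1.1 restricts the model's input to the DLT period, and Appendix 10, Section 1.1 fits it to the first five weeks of treatment. Sections 5.1.2.1 and 7.3.2 also say that later toxicities are weighed in dose-level decisions, can inform the model if sponsor, medical monitor and investigators agree, and count towards the maximum administered dose for the combination part.

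**The concern.** The two-dose requirement has a purpose. On schedule, the window contains the first dose, the second dose and about a week after it. The exception keeps the dose count but drops the link to the window. On its wording, a late participant becomes eligible on the day of the second dose, with no follow-up after that dose required, and enters the binomial denominator on the same footing as someone observed after both doses.

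The delays need not be random. Section 7.3.4 withholds treatment for findings short of a DLT, such as low-grade pneumonitis or Grade 2 liver, creatinine, bowel or neurological events. The participants with truncated observation may therefore be those already showing some toxicity. Cohorts have about three participants and a decision can follow two evaluable ones, so one classification matters. The study is open-label with no data monitoring committee, and no criterion guides the choice to include.

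**Working it through.** **Timing.** Inputs: dose 2 nominally on Day 29 (four-weekly dosing) and window end on Day 35 (Section 5.1.2.1). Day of dose 2 = 29 + delay; window days from dose 2 onward = max(0, 35 − day + 1).

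| Delay (days) | Day of dose 2 | Window days left | Handling |
|---|---|---|---|
| 0 | 29 | 7 | on time |
| 1–6 | 30–35 | 6 down to 1 | same visit |
| 7–12 | 36–41 | 0 | same visit |
| over 12 | next nominal visit, Day 57 | 0 | missed dose |

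Six of the 12 same-visit delay days give a participant with two doses in total but one inside the window. Day 41 is 40 days after dose 1, under six weeks (42 days), so Section 8.1 does not remove these participants. Day 57 is 56 days, or eight weeks, after dose 1, so longer delays mostly do lead to discontinuation. If the window is counted as 35 elapsed days, the affected delays are 8 to 12 days.

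**Model, reproduced first.** Appendix 10 gives logit(p) = log α + β·log(d/800), with (log α, log β) bivariate normal, means (−0.847, 0), SDs (1.53, 1) and correlation 0. A dose is a candidate only if P(DLT rate ≥ 33%) is below 0.30; among candidates, the one with the largest probability of lying in 16% to 33% is chosen. I used a binomial likelihood and integrated over a 1201 × 1201 grid.

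- Plug-in prior DLT rates at 25, 80, 200, 400 and 800 mg: 0.013, 0.041, 0.097, 0.176, 0.300. Stated: 0.01, 0.04, 0.1, 0.18, 0.30.
- Worked example in Appendix 10, Section 3 (0/3 at 25 mg, 1/3 at 80 mg): target probability 0.360 at 200 mg and 0.299 at 80 mg, against the stated 0.372 and 0.311 (0.012 apart in each case). As stated, 400 mg (overdose probability 0.468) and 800 mg (0.632) are excluded and 200 mg is recommended.

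**Same example, with one non-DLT participant at 80 mg having a second dose after Day 35.**

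| Treatment of that participant | Data at 80 mg | P(≥33%) at 80 mg | P(≥33%) at 200 mg | Recommended |
|---|---|---|---|---|
| Counted as DLT-free | 1/3 | 0.110 | 0.284 | 200 mg |
| Not evaluable | 1/2 | 0.160 | 0.348 | 80 mg |
| DLT after the late dose, counted | 2/3 | 0.381 | 0.629 | 25 mg |

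**Other configurations.**

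- 0/3 at 25 and 80 mg, then 1/3 versus 1/2 at 200 mg: overdose probability 0.096 versus 0.138 at 200 mg, and 0.304 versus 0.361 at 400 mg. Recommendation 200 mg either way, though 0.304 is only just above the limit.
- 0/3 at 25, 80 and 200 mg, then 1/3 versus 1/2 at 400 mg: 0.118 versus 0.168 at 400 mg, and 0.480 versus 0.533 at 800 mg. Recommendation 400 mg either way.

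**The case against.** The other side has four good points.

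- **Inclusion is a judgement.** The exception permits counting such a participant and does not require it. This stands. It limits the claim to what the rule allows, but with no criterion stated the denominator is not prespecified.
- **Late events are not ignored.** Sections 5.1.2.1 and 7.3.2 bring them into clinical review and, by agreement, into the model, and the BLRM guides the decision without dictating it. This also stands. But these routes add events and do not correct who is counted as DLT-free. The route into the model also sits awkwardly with Section 10.1.1's restriction to the DLT period.
- **The 1/2 comparison is not the effect of the fix.** A late participant who is followed and has no DLT stays in, and the data remain 1/3. Correct: 1/2 applies only when follow-up after dose 2 is lacking.
- **The second dose may carry less risk.** Section 3.2.2.4 reports that most infusion reactions come with the first infusion. For that toxicity the loss is smaller.

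A reader might go further and infer that Part A's DLT rates are biased downward by a known amount. The documents do not support that. They give no frequency of 7-to-12-day delays and no second-dose risk, so any percentage would rest on an assumed per-dose rate. A reader might also infer that missed doses leave the gap open without limit; the six-week rule in Section 8.1 closes most of that.

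**Conclusion.** The gap is real and follows from the protocol's own rules. Within ordinary delay handling, a participant can be entered in the BLRM as evaluable without a DLT when only one of the two required doses fell inside the window. The exposure is delays of 7 to 12 days, for a non-DLT reason, where the team chooses to include.

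The effect depends on the data. In the protocol's own example, one such participant decides whether 200 mg passes overdose control (0.284 against 0.348, limit 0.30). In the two other configurations checked, the recommendation does not move. It would therefore be wrong to conclude that every such inclusion alters escalation.

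The figures assume the Appendix 10 prior, a binomial likelihood and hypothetical data. They are illustrations and not trial results. The point merits a correction before further escalation decisions, but does not call the design into question.

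**What to change.** This is a change to analysis evaluability only; nothing about dosing needs to change. In Section 7.3.2, state that a Part A participant with a delayed second dose enters the BLRM as evaluable without a DLT only once observed after that dose for as long as the nominal schedule provides (Days 29 to 35, about seven days). Any DLT in that extended individual window counts. A participant without that observation is non-evaluable and may be replaced under the existing rule in Section 7.1.1.

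Align Section 5.1.2.1 (the 35-day period and the cohort-decision trigger), Section 10.1.1 and Appendix 10, Section 1.1, so that the model's input period matches. The edit therefore touches several sections.

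The cost is an occasional later cohort decision: with dose 2 on Day 41, seven days' observation ends on Day 47, 12 days after Day 35, so up to about two weeks. The alternative cost is one replacement participant.
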